### 5.2.2.3 Analysis by subgroups

Descriptive analysis (number, % with its 95% confidence interval) will be performed in the FAS (primary imputation method) and among completers (Observed cases under treatment) as detailed in section 5.2.2.1 for the following subgroups of interest:

- Biopsy length at baseline ( $\leq 8$ ,  $>8$  mm)
- SAF-A score at baseline (A2-A3, A4)
- CRN-F score at baseline (F0-F1, F2-F3)
- NAS score at baseline ( $<6$ ,  $\geq 6$ )
- BMI at baseline (Obese, Non-obese)
- Metabolic syndrome at baseline (Yes, No)
- Insulin-resistance status at baseline (Yes, No)
- Sex (Male, Female)

### 5.2.2.4 Secondary analyses of the primary endpoint

#### **Dose-response relationship**

Moreover, the dose-response relationship will be assessed on the FAS (Primary imputation method and Observed cases under treatment), and on the PP (Observed cases under treatment) according to method detailed in section 4.1.5 (Cochran-Armitage test using PROC LOGISTIC with adjustment on diabetic status).

#### **Evaluation of dose effect (1200 mg vs. 800 mg)**

Lanifibranor 1200 mg will be compared to lanifibranor 800 mg using a CMH test stratified on the diabetic status. The same methodology as the one defined in the section 5.2.2.1 (paragraph ‘Evaluation of treatment effect (each dose versus placebo)’) will be implemented.

### **Generalizability of the treatment effect: Evaluation of any “site” effect**

In order to explore any potential “site” effect on primary criterion, same analysis as those detailed in section 5.2.2.1 will be performed with a stratification on site (after regrouping as defined in section 4.1.7) instead of a stratification on diabetic status. Heterogeneity of results across sites will be tested through the Breslow-Day test (see section 4.1.7).

The two strategies of site regrouping will be used to explore this potential “site” effect as detailed in section 4.1.7.

The population of analysis will be the FAS as described in section 4.3.3. The primary imputation method described in section 4.1.6.3 will be used for missing data replacement.

In a first time, analysis will be done considering all patients. Then it will be repeated on diabetic patients and on non-diabetic patients.

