### **9.3 Randomization**

Patients will be randomized equally 1:1:1 to either dose of lanifibranor or placebo stratified on presence/absence of diabetes. Strata will be self-weighted *i.e.* patients meeting inclusion/exclusion criteria will be recruited as they come (no quota).

The randomization list will be setup with blocs of size equal to 6.

After identification with a login and a password, the randomization process will be provided through an Interactive Web Response System (IWRS) integrated to the eCRF. Once a set of medical characteristics are entered, the system lets you know immediately, which medication kit to use for this particular patient.

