The generalizability of the treatment effect across geographical area will be tested and the statistical strategy will be defined in the SAP once the sample size will be known by stratum and country and before the break of the randomization code.

There is no planned interim analysis for success. However, the DSMB may decide to perform some futility analyses in particular in case of safety concerns.

A series of sensitivity analyses will be performed to assess the robustness of results such as the use of a stratified test (country as a stratification factor), the use of other sets of patients (PP set, Evaluable set, Randomized set, completer set). In case of missing assessment at W24, the patient will be considered a non-responder. A responder is consequently a confirmed responder.

Secondary efficacy analyses:

- NASH improver rates in each dose will be compared to placebo using the Cochran Mantel Haenszel test stratified on diabetes.
- Percent of patients with resolution of NASH in each dose will be compared to placebo using the Cochran Mantel Haenszel test stratified on diabetes.
- Percent of patients with a change in components of SAF score in each dose will be compared to placebo using the Cochran Mantel Haenszel test stratified on diabetes.
- Percent of patients with at least 1-point improvement of fibrosis without worsening of NASH in each dose will be compared to placebo using the Cochran Mantel Haenszel test stratified on diabetes.

Planned exploratory analyses:

- Inflammatory markers (fibrinogen, hs-CRP, alpha2 macroglobulin and haptoglobin levels) change from baseline to end of treatment (week 24) will be compared using GLM with the diabetes and dose as covariates. A mixed model for repeated measures will also be used to compare the time course of the response of each treatment group.
- Transient Elastography and Controlled Attenuation Parameter change from baseline to end of treatment (week 24) will only be described.
- Glucose metabolism (fasting glucose and insulin, HOMA index and, in subjects with T2DM, HbA1c) change from baseline to end of treatment (week 24) will be compared using GLM with the diabetes

and dose as covariates. A mixed model for repeated measures will also be used to compare the time course of the response of each treatment group.

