## 4.2 Sample size calculation

The expected rate of responders according to the retained definition was estimated to 10% for the placebo by a group of clinical experts. An excess rate of responders of 20% was accepted as clinically pertinent. It corresponds to a multiplication of chance of success (responders) of 3 and a NNT (Number Needed to Treat) of 5. The sample size required to reach a power of at least 80% is 72 patients per group with a two-sided alpha of 0.025 (adjustment for multiplicity). The sample size is sensitive to the rate of responders in the placebo group. For example, if the rate of responders is 15% instead of 10% then 85 patients are required. If the true rate is lower than 10% then less patients may be sufficient. The sample size is therefore rounded in the conservative side of 75 patients per group.

Based on the experience of previous clinical trials, it is estimated that 100 patients per group will need to be screened to randomise 75 patients after central reading of liver biopsy confirms the NASH diagnosis and activity (screening failure rate of 25%). However, as detailed in section 3.5, the observed screening failure rate was of 72%), consistent with all other clinical trial performed in NASH with such a high screening failure rate.

In case the end of study liver biopsy slides are not available or not interpretable in more than 5% of patients, an amendment will be submitted to increase sample size accordingly.

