#### **Evaluation of treatment effect (each dose versus placebo)**

Each treatment dose will be compared to placebo using a CMH test stratified on the diabetic status.

In order to take into account multiplicity of tests, the ascending Hochberg procedure will be applied (see section 4.1.5 for details). The p-values of the 2 tests will be provided and will provide conclusions regarding the primary objective of the study met or not met.

Corresponding CMH Odds ratio (OR) and adjusted-Relative Risk (RR) will be provided with their 95% confidence intervals, in the FAS for the two lanifibranor groups.

The Breslow-Day test will be implemented for homogeneity of the odds ratios between diabetic and non-diabetic patients:

- If the test is significant, then this means that the treatment effect has not the same magnitude in diabetic and non-diabetic patients (significant difference in OR in the 2 populations)
- If the test is not significant, then this means that the treatment effect has the same magnitude in diabetic and non-diabetic patients (no significant difference in OR in the 2 populations).
- Regardless the significance of the test, both OR and RR in diabetic and non-diabetic patients will be provided with their 95% confidence interval

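### The all-patient site-effect CMH replaces diabetes with site group, so its pooled odds ratio can move for a reason other than site; the loss of power is small

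*SAP*

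**What the plan says.** Protocol 9.3 sets the randomisation: "Patients will be randomized equally 1:1:1 to either dose of lanifibranor or placebo stratified on presence/absence of diabetes". The primary test in SAP 5.2.2.1 follows it: "Each treatment dose will be compared to placebo using a CMH test stratified on the diabetic status". SAP 4.1.5 makes the diabetes-stratified CMH the general method for binary endpoints and names the CMH odds ratio as the primary measure of effect. Within SAP 5.2.2.4, the dose-response, dose-effect and weight-adjusted analyses all keep diabetic status.

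The site analysis in the same section does not. Its aim is stated as "In order to explore any potential “site” effect on primary criterion", and it is to be run "with a stratification on site (after regrouping as defined in section 4.1.7) instead of a stratification on diabetic status". No reason is given for the substitution. The section continues: "Then it will be repeated on diabetic patients and on non-diabetic patients". Heterogeneity across site groups goes to the Breslow-Day test.

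SAP 4.1.7 defines two groupings: Bulgaria against all other countries, and three groups by number of patients treated. (It announces three strategies but lists two; 5.2.2.4 speaks of two.)

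Protocol 9.7.4 leaves the geographical strategy to the SAP. It also names a country-stratified sensitivity test, without saying whether diabetes stays in.

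**The concern.** A site analysis is read against the primary result: does the answer change once site is taken into account? That reading is clean only if site is the sole difference. Here a second thing changes, because the stratification factor of the randomisation is removed. If diabetes predicts response, the pooled odds ratio moves for that reason alone, and a reader could take the movement for a site effect. Leaving out a prognostic stratum also costs some power.

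Sparse tables are the reason Protocol 9.7.4 gives for ignoring centre in the primary analysis. After pooling to 2 or 3 site groups, crossing with diabetes gives only 2 × 2 = 4 or 3 × 2 = 6 strata, so the number of strata does not prevent a pooled CMH that uses both factors.

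**Working it through.** **Inputs from the documents.** Placebo 10%, active 30%, two-sided alpha 0.025 per comparison, 72 rounded to 75 per group (SAP 4.2). 247 randomised 1:1:1, about 82 per arm (SAP 3.5). **Not in the documents, so assumed:** diabetes prevalence 30 to 50%, the prognostic odds ratio of diabetes, the site-group shares, and no effect of site on response.

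**The plan's own figure.** n = [p1(1−p1) + p2(1−p2)] × (z₀.₉₈₇₅ + z₀.₈₀)² / d², with (2.2414 + 0.8416)² = 9.505.
- 10% v 30%: 0.30 × 9.505 / 0.04 = 71.3, so 72.
- 15% v 35%: 0.355 × 9.505 / 0.04 = 84.4, so 85.

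Both stated sizes reproduce.

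**Shift in the odds ratio with no site effect.** Ignoring diabetes: (0.30/0.70) / (0.10/0.90) = 3.86. Now let 30% be diabetic with a prognostic odds ratio of 3. Placebo rates are 6.7% and 17.7% (0.7 × 6.7 + 0.3 × 17.7 = 10.0%). A common treatment odds ratio of 4.11 gives active rates of 22.8% and 46.9% (0.7 × 22.8 + 0.3 × 46.9 = 30.0%). The same trial therefore has an odds ratio of 3.86 without diabetes and 4.11 with it. Over 30 to 50% diabetics, the conditional value is 3.95 at a prognostic odds ratio of 2, about 4.1 at 3, and 4.3 to 4.5 at 5.

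For scale, the standard error of the log odds ratio at 82 per arm is √(1/8.2 + 1/73.8 + 1/24.6 + 1/57.4) = 0.44. The shifts are ln(3.95/3.86) = 0.02, ln(4.11/3.86) = 0.06 and ln(4.45/3.86) = 0.14, so at most about a third of a standard error.

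**Power.** Simulated CMH tests without continuity correction, one dose v placebo, 82 per arm, diabetes balanced by stratified randomisation, 100,000 trials per row (error about 0.1 point):

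| Site groups | Diabetics | Prognostic OR | Site only | Site × diabetes | Difference |
|---|---|---|---|---|---|
| 2 (20/80%) | 30% | 1 | 84.74% | 84.44% | −0.30 |
| 2 | 30% | 2 | 85.16% | 85.32% | +0.16 |
| 2 | 30% | 3 | 85.58% | 86.50% | +0.92 |
| 2 | 30% | 5 | 86.15% | 88.30% | +2.15 |
| 2 | 30% | 0.2 | 85.30% | 86.41% | +1.11 |
| 3 (30/35/35%) | 40% | 1 | 84.81% | 84.28% | −0.53 |
| 3 | 40% | 3 | 85.38% | 86.05% | +0.67 |
| 3 | 40% | 5 | 86.04% | 87.87% | +1.83 |

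At 75 per arm the gain reaches 2.45 points at a prognostic odds ratio of 5.

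Two scenarios with fixed rates (20,000 trials, 25% of patients in one site group, 40% diabetics; rates given as non-diabetic/diabetic):
- Placebo 5/20%, active 20/45%: 80.3% v 82.0%. The placebo prognostic odds ratio is (0.20/0.80) / (0.05/0.95) = 4.75.
- Placebo 10/30%, active 25/55%: 70.1% v 72.9%. The placebo prognostic odds ratio is 3.86. The overall placebo rate is 0.6 × 10 + 0.4 × 30 = 18%, above the planned 10%.

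Over 30 to 50% diabetics the gain in these two is 1.7 to 3.0 points.

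**Type I error (40% diabetics).** Site only rejects 2.2% of the time at a prognostic odds ratio of 3 and 2.0% at 5, against a nominal 2.5%. Spreading diabetes unevenly over the site groups gave the same picture.

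**Precision of the planned repeats.** With 30 to 50% diabetics and 10% v 30% in each subset, power is about 31 to 51% in diabetics and 51 to 67% in non-diabetics.

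**The case against.** The best defence is that the plan already contains a like-for-like comparison. SAP 5.2.2.1 reports odds and risk ratios separately in diabetic and non-diabetic patients whatever the Breslow-Day result, and 5.2.2.4 repeats the site analysis in the same two subsets. Inside each subset only site changes. This stands: a reader might infer that the plan cannot isolate site at all, and that is not so. What is missing is a pooled version with useful precision.

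Power is also a weak yardstick here. The analysis is exploratory, has no power target and does not decide whether the primary objective is met. The figures above concern the treatment test, not the detection of site heterogeneity, whose power was not computed. A reader might infer a material loss; the documents give no prognostic effect for diabetes, and only a strong one costs more than about 1 point. Nor is the comparison confounded or the type I error inflated, since stratified randomisation balances diabetes across arms.

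Sparseness cannot be dismissed. If one site group holds 25% of patients, it has about 82 × 0.25 = 20 per arm. With half of them diabetic, a cell holds about 10 placebo patients and, at a 10% rate, 1 expected responder. CMH tolerates that; Breslow-Day does not. Breslow-Day across the combined strata would also mix site heterogeneity with diabetes heterogeneity.

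Finally, a reader might take the protocol's country-stratified test as a second instance. Protocol 9.7.4 does not say that diabetes is dropped there.

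The odds-ratio argument has a limit too: a risk ratio estimated directly, as the SAP prefers where the log-binomial model converges, is collapsible. The shift concerns the odds ratio and any risk ratio converted from it.

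**Conclusion.** The point holds as a minor one. The all-patient site analysis drops the randomisation stratum and so changes two things at once. Its pooled odds ratio can differ from the primary one with no site effect, by about 0.1 to 0.6 on a value near 3.9 for prognostic odds ratios of 2 to 5. The within-diabetes repeats deal with this only at lower precision, and no pooled analysis adjusts for both factors.

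The loss of power is about 0.2 points at a prognostic odds ratio of 2, up to 1 point at 3 and about 2 to 3 points at 4 to 5. These figures rest on assumed prevalence, prognostic strength and site shares. The primary test keeps diabetes, and its conclusion is unaffected.

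**What to change.** In SAP 5.2.2.4:
- Stratify the pooled site CMH on site group by diabetic status, giving 4 strata for the first grouping and 6 for the second. Any difference from the primary result is then due to site.
- Keep the planned repeats in diabetic and in non-diabetic patients.
- Test site heterogeneity with a treatment-by-site-group term in a logistic model that includes treatment, site group and diabetic status, in place of Breslow-Day across the combined strata.
- If the protocol's country-stratified test is run, state whether diabetes stays in.

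The cost is one additional model, possibly sparse cells in the smaller site group, and about 0.2 to 0.5 points of power if diabetes turns out not to be prognostic. No new data are needed.

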### **Evaluation of treatment effect after adjustment on the relative change in weight from baseline**

In order to evaluate the treatment effect after adjustment on the relative change in weight from baseline, a LOGISTIC model will be run on the FAS - Observed Cases under treatment. For this model, treatment will be considered as a quantitative covariate (placebo, 800 mg and 1200mg), diabetic status as a qualitative covariate (Presence, Absence) and weight variation as a quantitative effect. The p-value assessing the significant dose-response relationship at week 24 will be provided based on this model, as well as the OR for a change of 2% in weight.

### 5.2.3 Secondary analyses

#### 5.2.3.1 NASH improvement

The endpoint will be a binary variable (Improver / Non-improver) based on the change from baseline to Week 24 of the CRN NAS score (see section 4.5.4.1.7).

#### **Main analysis**

The population of analysis will be the FAS as described in section 4.3.3. The primary imputation method described in section 4.1.6.3 will be used for missing data replacement.

- Descriptive analysis

The number (% with its 95% confidence interval) of improvers and non-improvers at Week 24 will be summarized in a table using descriptive statistics by treatment group and diabetic status. The reason for non-improvement (No decrease of 2 points of NAS score, Worsening of CRN-F score, Both, No post-treatment biopsy available) will also be displayed.

- Evaluation of treatment effect (each dose versus placebo)

The same methodology as the one defined in the section 5.2.2.1 (paragraph ‘Evaluation of treatment effect (each dose versus placebo)’ ) will be implemented.

- Evaluation of dose effect (1200 mg vs. 800 mg)

Lanifibranor 1200 mg will be compared to lanifibranor 800 mg using a CMH test stratified on the diabetic status. The same methodology as the one defined in the section 5.2.2.4 (paragraph ‘Evaluation of dose effect (1200 mg vs. 800 mg)’ ) will be implemented.

- Dose-response relationship

The dose-response relationship will be assessed on the FAS (Primary imputation method and Observed cases under treatment), and on the PP (Observed cases under treatment) according to method detailed in section 4.1.5 (Cochran-Armitage test using PROC LOGISTIC with adjustment on diabetic status).

#### **Sensitivity analyses**

Several sensitivity analyses will be performed as detailed in table below. Each time, descriptive analysis, evaluation of treatment effect (each dose versus placebo) and evaluation of dose effect will be performed as detailed above for main analysis.

Analysis population	Treatment group	Missing data replacement
FAS	Actual treatment received	Observed cases under treatment*
PP	Actual treatment received	Observed cases under treatment
EPP	Actual treatment received	Secondary imputation method

\* This analysis corresponds to analyses on completers (biopsy at week 24 performed, within maximum 14 days after last intake).

### **Analysis by subgroups**

Descriptive analysis (number, % with its 95% confidence interval) will be performed in the FAS (primary imputation method) and among completers (Observed cases under treatment) as detailed in section 5.2.2.1 for the following subgroups of interest:

- NAS score at baseline ( $<6$ ,  $\geq 6$ )

#### *5.2.3.2 Resolution of NASH without worsening of fibrosis*

The endpoint will be a binary variable (responder / non responder) based on the CRN-I and CRN-B scores at Week 24 and the change in CRN-F score from Baseline to Week 24 (see section 4.5.4.1.8).

### **Main analysis**

The population of analysis will be the FAS as described in section 4.3.3. The primary imputation method described in section 4.1.6.3 will be used for missing data replacement.

- Descriptive analysis

The number (% with its 95% confidence interval) of responders and non-responders at Week 24 will be summarized in a table using descriptive statistics by treatment group and diabetic status.

The reason for non-response (CRN-Inflammation  $> 1$ ,  $\pm$  CRN-Ballooning  $> 0$ ,  $\pm$  Worsening of CRN-F score, No post-treatment biopsy available) will also be displayed.

- Evaluation of treatment effect (each dose versus placebo)

The same methodology as the one defined in the section 5.2.2.1 (paragraph ‘Evaluation of treatment effect (each dose versus placebo)’ ) will be implemented.

- Evaluation of dose effect (1200 mg vs. 800 mg)

Lanifibranor 1200 mg will be compared to lanifibranor 800 mg using a CMH test stratified on the diabetic status. The same methodology as the one defined in the section 5.2.2.4 (paragraph ‘Evaluation of dose effect (1200 mg vs. 800 mg)’ ) will be implemented.

- Dose-response relationship

Moreover, the dose-response relationship will be assessed on the FAS (Primary imputation method and Observed cases under treatment), and on the PP (Observed cases under treatment) according to method detailed in section 4.1.5 (Cochran-Armitage test using PROC LOGISTIC with adjustment on diabetic status).

**Sensitivity analyses**

Several sensitivity analyses will be performed as detailed in table below. Each time, descriptive analysis, evaluation of treatment effect (each dose versus placebo), evaluation of dose effect (1200 mg vs. 800 mg) will be performed as detailed above for main analysis.

Analysis population	Treatment group	Missing data replacement
FAS	Actual treatment received	Observed cases under treatment*
PP	Actual treatment received	Observed cases under treatment
EPP	Actual treatment received	Secondary imputation method

\* This analysis corresponds to analyses on completers (biopsy at week 24 performed, within maximum 14 days after last intake).

**Analysis by subgroups**

Descriptive analysis (number, % with its 95% confidence interval) will be performed in the FAS (primary imputation method) and among completers (Observed cases under treatment) as detailed in section 5.2.2.1 for the following subgroups of interest:

- Biopsy length at baseline ( $\leq 8$ ,  $>8$  mm)
- SAF-A score at baseline (A2-A3, A4)
- CRN-F score at baseline (F0-F1, F2-F3)
- NAS score at baseline ( $<6$ ,  $\geq 6$ )
- BMI at baseline (Obese, Non-obese)
- Metabolic syndrome at baseline (Yes, No)
- Insulin-resistance status at baseline (Yes, No)
- By site group No. 1 (Bulgaria, all other countries)
- By site group No. 2 (3 or less patients randomised and treated, from 4 to 9 patients randomised and treated, 10 or more patients randomised and treated)
- Sex (Male, Female)

**5.2.3.3 Improvement of fibrosis by at least 1 stage with no worsening of NASH**

The endpoints will be a binary variable (responder / non responder) based on the change from baseline to Week 24 of the CRN-F score and the worsening of NASH (see section 4.5.4.1.9).

**Main analysis**

The population of analysis will be the FAS as described in section 4.3.3. The primary imputation method described in section 4.1.6.3 will be used for missing data replacement.

- Descriptive analysis

The number (% with its 95% confidence interval) of responders and non-responders at Week 24 will be summarized in a table using descriptive statistics by treatment group and diabetic status.

The reason for non-response (Worsening of CRN-S score,  $\pm$  Worsening of CRN-I score,  $\pm$  Worsening of CRN-B score,  $\pm$  No improvement of CRN-F score, No post-treatment biopsy available) will also be displayed.

- Evaluation of treatment effect (each dose versus placebo)

The same methodology as the one defined in the section 5.2.2.1 (paragraph ‘Evaluation of treatment effect (each dose versus placebo)’) will be implemented.

- Evaluation of dose effect (1200 mg vs. 800 mg)

Lanifibranor 1200 mg will be compared to lanifibranor 800 mg using a CMH test stratified on the diabetic status. The same methodology as the one defined in the section 5.2.2.4 (paragraph ‘Evaluation of dose effect (1200 mg vs. 800 mg)’) will be implemented.

- Dose-response relationship

Moreover, the dose-response relationship will be assessed on the FAS (Primary imputation method and Observed cases under treatment), and on the PP (Observed cases under treatment) according to method detailed in section 4.1.5 (Cochran-Armitage test using PROC LOGISTIC with adjustment on diabetic status).

